12.2 Derived and Transformed Data

Baseline will be considered to be the latest value obtained before study drug administration (e.g. Day 0, pre-dose; or Day -1 if not recorded pre-dose; or Screening if not recorded elsewhere (e.g. body weight)).

Laboratory data will be reported in standard units. Out-of-range laboratory tests may be repeated. If a test is out-of-range at a baseline time point and repeated before dosing, the latest repeat value before dosing will be used as baseline. However, if a test is out-of-range and repeated at any other time during the study, the out-of-range value (not the repeat value) will be included in statistical summaries.

TriPLICATE ECG and vital sign measurements will be made at pre-dose on Day 0 and the mean of the three measurements for each subject will be used as their baseline value for that session.

The pharmacokinetic parameters to be derived are given in Appendix B.

12.3 Assessment Windows

No assessment windows are defined for this report.

12.4 Values of Potential Clinical Importance

Any laboratory value outside the reference interval for that variable will be flagged with an 'H' if it is higher than the reference interval, and with an 'L' if it is lower. Additionally, if, during the course of the trial, a variable changes from baseline (Day 0 pre-dose) by more than a predetermined amount (as defined by the Principal Investigator, Appendix A), that value will receive a flag 'I' if increased, or 'D' if decreased. Therefore, if a value both falls outside the reference interval and alters from the baseline value by more than the predetermined amount, it will attract a double flag and will be considered to be potentially clinically important.

A vital signs result will be considered to be of potential clinical importance if it falls outside the relevant range below:

Vital Sign	Range
Supine/semi-recumbent systolic blood pressure	85–160 mm Hg
Supine/semi-recumbent diastolic blood pressure	40–90 mm Hg
Supine/semi-recumbent heart rate	35–100 beats/min
Respiration rate	8–20 per min
Oral temperature	35.5–37.8°C

QT, QTcB or QTcF > 450 msec and increases in QT, QTcB or QTcF from baseline (Day 1 pre-dose) of > 30 msec will be considered to be potentially clinically important.

13 Study Population

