Toxicokinetic data were obtained from Good Laboratory Practice (GLP) 4-week repeated dose studies in rats and dogs. In rats, exposure was slightly less than dose-proportional after oral administration. In dogs, the toxicokinetics showed a more than dose proportional increase in AUC_{0-24h} and C_{max} (5 – 20 mg/kg).

Summary of toxicology data

A comprehensive battery of repeated dose studies was conducted, in which, emodepside was orally applied (in diet) for up to 13 and 14 weeks in mice and rats, respectively, at doses up to 1000 ppm and 800 ppm (1000 ppm equals in mice approx. 245 – 380 mg/kg, 800 ppm equals in rats approx. 77 – 95 mg/kg, both in 13-week treatment schedule).

The studies in rats revealed toxicities resulting from metabolic changes induced by emodepside indirectly, such as a decrement in bodyweight gain, but, in parallel, an

increased feed and water consumption as well as deformation of teeth as a sign of a diabetic-like effect. The main affected organs were kidney, pancreas and liver, with associated changes in haematological parameters, triglyceride and glucose levels in the plasma and lipid and glycogen stores. These toxicological findings pointed to a diabetes-related condition (inhibition of insulin secretion followed by increased glucose levels and reduced leptin levels, as confirmed by mechanistic studies). In mice, the NOAEL after 14 weeks of treatment was 50 ppm (10.5 – 16.8 mg/kg). The NOAEL in the 14-week rat study was defined at 10 ppm (m: 0.73, f: 1.11 mg/kg/day). In 4-week rat studies, 50 ppm (equals 4 – 5 mg/kg) was defined as the NOAEL.

In dogs, doses starting from 10 mg/kg per day for 4 weeks resulted in clinical signs like vomiting, tremor and unsteady gait. At 20 mg/kg, an effect on nutritional state, food intake and bodyweight gain was noted. All effects were reversible after a recovery period of 4 weeks. The NOAEL for this study was 5 mg/kg.

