11.6.2. Haematology, Coagulation and Clinical Chemistry Parameters

Data from haematology, coagulation and clinical chemistry will be summarised by treatment.

Any laboratory value outside the reference interval for that variable will be flagged with an 'H' if it is higher than the reference interval, and with an 'L' if it is lower. Additionally, if, during the course of the trial, a variable changes from baseline by more than a predetermined amount (as defined by the Principal Investigator), that value will receive a flag 'I' if increased, or 'D' if decreased. Therefore, if a value both falls outside the reference interval and alters from the baseline value by more than the predetermined amount, it will attract a double flag and will be considered to be potentially clinically important.

All laboratory values of potential clinical importance will be listed. In a separate listing, laboratory values of potential clinical importance will be listed with all related laboratory results (i.e. haematology or clinical chemistry). Frequencies of laboratory values of potential clinical importance will be summarised.

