4.2.2 Secondary Endpoints

- Safety and Tolerability Variables:
 - Adverse Events (AEs)
 - Physical and neurological examination findings
 - Vital signs (BP and HR),
 - 12-lead ECG (HR, PR, QRS, QTcB, QTcF), will be analysed ad hoc for safety and for the final data base and report by central reading
 - Clinical laboratory tests
 - Haematology: haemoglobin, haematocrit, mean corpuscular volume (MCV), mean corpuscular haemoglobin (MCH), mean corpuscular haemoglobin concentration (MCHC), platelets, reticulocytes, white blood cells (WBC) including differential, red blood cells (RBC);
 - Coagulation: activated partial thromboplastin time (aPTT), prothrombin time (PT);
 - Biochemistry: serum aspartate aminotransferase (AST), alanine aminotransferase (ALT), alkaline phosphatase (AP), gamma-glutamyl transpeptidase (GGT), lactate dehydrogenase (LDH), creatine kinase (CK), amylase, lipase, glucose, cholesterol (HDL, LDL, total), triglycerides, creatinine, urea, uric acid, bilirubin (total and conjugated), total protein, sodium, potassium, calcium, chloride and magnesium;
 - Urinalysis: by dipstick – glucose, ketone bodies, specific gravity, occult blood, pH, proteins, leucocytes, bilirubin, urobilinogen, nitrites, and microscopy (reflex).

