16.2.3	Analysis sets, including subjects excluded from analysis	
16.2.3.1	Listing of Analysis Populations	L AN1 PG
16.2.4	Demographic data & concomitant medication	
16.2.4.1	Listing of Demographic Characteristics	L DM1 PG
16.2.4.2	Listing of Concomitant Medications	L CM1 PG
16.2.5	Study drug administration	
16.2.5.1	Listing of Exposure Data	L EX1 PG
16.2.6	Pharmacokinetic and pharmacodynamic data	
16.2.6.1	Listing of Emodepside Plasma Pharmacokinetic Concentration-Time Data	L PK1 PG
16.2.6.2	Listing of Derived Emodepside Plasma Pharmacokinetic Parameters	L PK4 PG
16.2.6.3	Individual Emodepside Plasma Concentration-Time Plots (log scale) for Estimation of λ_z , with Regression Line	F PK10
16.2.7	Adverse events	
16.2.7.1	Listing of All Adverse Events	L AE1 PG
16.2.7.2	Listing of Serious Adverse Events	L AE1 PG
16.2.7.3	Listing of Adverse Events Leading to Withdrawal from Study	L AE1 PG
16.2.8	Laboratory values	
16.2.8.1	Listing of Clinical Chemistry Abnormalities of Potential Clinical Importance	L LB1 PG
16.2.8.2	Listing of All Clinical Chemistry Laboratory Data for Subjects with PCI Abnormalities*	L LB2 PG
16.2.8.3	Listing of Haematology Abnormalities of Potential Clinical Importance	L LB1 PG
16.2.8.4	Listing of All Haematology Laboratory Data for Subjects with PCI Abnormalities*	L LB2 PG
16.2.8.5	Listing of Urinalysis Data	L URI PG
16.2.9	Vital signs, ECG variables, physical and neurological findings	
16.2.9.1	Listing of Vital Signs of Potential Clinical Importance	L VS1 PG
16.2.9.2	Listing of ECG Values of Potential Clinical Importance	L EG1 PG

Listing	Description	Template (Shells below)
16.2.9.3	Listing of Abnormal ECG Findings	L EG2 PG
16.2.9.4	Listing of Abnormal Physical Examination Findings	L PE1 PG
16.2.9.5	Listing of Abnormal Neurological Examination Findings	L NE1 PG

* ICH does not require full listings of lab data so only subjects with double-flagged values will be listed.

Complete listings of all data collected in this study will also be produced.

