Appendix A: Laboratory Ranges

Pre-determined Changes for Laboratory Data (from FL140 v3)

Test	Test Code	Unit	Sex	Delta ranges	
				Acceptable decrease	Acceptable increase
Activated partial thromboplastin time	APTTT	sec	Both	- 8.0	+ 8.0
Alanine transferase	ALTN	IU/L	F	-	+ 30
Alanine transferase	ALTN	IU/L	M	-	+ 30
Albumin	ALB	g/L	Both	- 8	+ 8
Alkaline phosphatase	ALPN	IU/L	Both	- 30	+ 30
Amylase	AMY	U/L	Both	-	+ 150
Aspartate transferase	ASTN	IU/L	F	- 30	+ 30
Aspartate transferase	ASTN	IU/L	M	- 30	+ 30
Basophils	BASO	10 ⁹ /L	Both	-	+ 0.30
Bilirubin conjugated	DBIL	µmol/L	Both	-	+ 4.0
Bilirubin total	TBIL	µmol/L	F	- 20.0	+ 10.0
Bilirubin total	TBIL	µmol/L	M	- 20.0	+ 10.0
Bilirubin unconjugated	IBIL	µmol/L	Both	-	-
C-reactive protein	CRP	mg/L	Both	-	-
CK relative index	CKMBR	%	Both	-	-
Calcium	CA	mmol/L	Both	- 0.4	+ 0.4
Carbon dioxide	CO2	mmol/L	Both	- 8	+ 8
Chloride	CL	mmol/L	Both	- 10	+ 10
Cholesterol	CHOL	mmol/L	Both	-	+ 0.7
Creatine kinase	CK	IU/L	F	-	+ 400
Creatine kinase	CK	IU/L	M	-	+ 400
Creatinine	CREA	µmol/L	Both	-	+ 40
Creatinine (DOA urine)	CREDA-U	mmol/L	Both	-	-
Eosinophils	EOS	10 ⁹ /L	Both	-	+ 0.50
Erythrocyte sedimentation rate	ESR	mm/h	Both	-	-
Fibrinogen	FIB-C	g/L	Both	-	-
Free T3	FT3	pmol/L	Both	- 3.5	+ 3.5
Free T4	FT4	pmol/L	Both	- 15.0	+ 15.0
Gamma glutamyl transferase	GGT	IU/L	F	-	+ 40
Gamma glutamyl transferase	GGT	IU/L	M	-	+ 40
Globulin	GLOB	g/L	Both	- 8	-
Glucose	GLU	mmol/L	Both	- 1.5	+ 2.5
Haematocrit	HCT	L/L	Both	- 0.050	-
Haemoglobin	HB	g/L	Both	- 20	-
High density lipoprotein	HDL	mmol/L	Both	- 1.50	+ 1.50
International normalised ratio	INRR	ratio	Both	-	-
Lactate dehydrogenase	LDH	IU/L	Both	-	+ 150
Lymphocytes	LYMP	10 ⁹ /L	Both	- 1.50	+ 1.50
Magnesium	MG	mmol/L	Both	-	-
Mean cell haemoglobin	MCH	pg	Both	- 2.0	+ 2.0
Mean cell haemoglobin concentration	MCHC	g/L	Both	- 25	+ 25
Mean cell volume	MCV	fL	Both	- 10	+ 10

Test	Test Code	Unit	Sex	Delta ranges	
				Acceptable decrease	Acceptable increase
Monocytes	MONO	10 ⁹ /L	Both	- 0.50	+ 0.50
Neutrophils	NEUT	10 ⁹ /L	Both	- 2.00	+ 8.00
Phosphate	PHOS	mmol/L	Both	- 1.00	+ 1.00
Platelets	PLT	10 ⁹ /L	Both	- 100	+ 100
Platelets (citrate tube)	PLTC	10 ⁹ /L	Both	- 100	+ 100
Potassium	K	mmol/L	Both	- 0.8	+ 0.8
Prolactin	PROL	µg/L	Both	-	-
Prothrombin time	PTT	sec	Both	- 4.0	+ 4.0
Red blood cells	RBC	10 ¹² /L	Both	- 1.0	-
Reticulocyte	RET	%	Both	-	-
Reticulocyte count	RETC	10 ⁹ /L	Both	-	-
Reticulocyte manual count	RETM	10 ⁹ /L	Both	-	-
Sodium	NA	mmol/L	Both	- 8	+ 8
Thrombin time	TT	sec	Both	-	-

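### Lipase, LDL cholesterol, magnesium and reticulocytes have no change limit in SAP Appendix A, so they can never count as potentially clinically important, and Table 14.3.4 would show zero for them whatever the results

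*SAP*

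**What the plan says.** SAP 12.4 uses two flags. A value outside the reference interval is marked H or L. A value that moves from baseline by more than a preset amount is marked I or D. A value is PCI "if a value both falls outside the reference interval and alters from the baseline value by more than the predetermined amount". The amounts are "as defined by the Principal Investigator, Appendix A", and that appendix is headed "Pre-determined Changes for Laboratory Data". Protocol 11.6.2 has the same two-flag rule, with no table of amounts.

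SAP 4.2.2 names the blood tests that are secondary safety endpoints. The biochemistry list includes "creatine kinase (CK), amylase, lipase, glucose, cholesterol (HDL, LDL, total), triglycerides" and ends with magnesium; the haematology list includes reticulocytes.

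The PCI displays depend on the double flag. The shell for Table 14.3.4 (T_LB1) counts HI and LD values beside the number of results and is to be repeated for all tests. The shell for the PCI listings (L_LB1_PG) is restricted to double-flagged subjects. A footnote to the listings in SAP 17.1 says "ICH does not require full listings of lab data so only subjects with double-flagged values will be listed", and the text after it adds that complete listings of all data will also be produced.

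**The concern.** A rule that needs a change limit cannot work for a test that has none, and the SAP gives no fallback. Table 14.3.4 would show such a test with a true number of results and a PCI count of zero. That zero means the rule could not be applied, but a reader would take it to mean that nothing was found.

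This matters most for lipase. On the rat studies, Protocol 1.3 says "The main affected organs were kidney, pancreas and liver", and lipase is one of the two pancreatic enzymes measured. The argument does not extend to LDL, magnesium or reticulocytes.

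A second gap concerns coagulation. SAP 14.5 promises a listing of every PCI laboratory value, but the PCI listings cover chemistry and haematology only.

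**Working it through.** The plan gives no figure to reproduce. The check sets the tests in SAP 4.2.2 against the rows of Appendix A and then applies SAP 12.4.

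**Step 1: count the tests.** SAP 4.2.2 gives 40 blood tests if the white-cell differential is counted as five (basophils, eosinophils, lymphocytes, monocytes, neutrophils). That count is an assumption; the documents say only that the differential is included.

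**Step 2: classify by Appendix A limit.**

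| Limit in Appendix A | Tests |
|---|---|
| Decrease and increase | 21 |
| Increase only | 11 |
| Decrease only | 4 |
| Row present, dash both ways | 2 (magnesium; reticulocytes, in all three of their rows) |
| No row | 2 (lipase, LDL) |

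21 + 11 + 4 + 2 + 2 = 40. So 36 tests have at least one limit and 4 have none (4/40 = 10%). The alphabetical list runs from lactate dehydrogenase straight to lymphocytes, and no break in the extracted table falls there, so lost text is an unlikely explanation.

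**Step 3: apply the rule.** PCI = (H or L) and (I or D).
- ALT has an increase limit of +30 IU/L. A value above the reference interval and more than 30 IU/L above baseline gets H and I, and is PCI.
- Lipase has no limit. A value of any size above the reference interval gets H, but I cannot be assigned, so it is not PCI. The same holds for LDL, magnesium and reticulocytes.

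SAP 12.4 describes no other route to PCI for laboratory values, and the shells count or list double flags only.

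**Step 4: size.** Protocol Table 4 plans 7 samples per subject for haematology and for biochemistry. Taking away screening and pre-dose leaves 7 − 2 = 5 after dosing. With up to 84 subjects, each test has up to 5 × 84 = 420 post-dose results, and the four together have 4 × 420 = 1,680. If only one treatment is tested in Part 2, there are 72 subjects and 4 × 5 × 72 = 1,440 results. None could be PCI.

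**Step 5: coagulation.** Appendix A gives ±8.0 s for aPTT and ±4.0 s for PT, so both can be double-flagged. Table 14.3.4 cites only Listings 16.2.8.1 (chemistry) and 16.2.8.3 (haematology), and no coagulation PCI listing is specified. Reading coagulation as part of haematology does not fit, because SAP 4.2.2, SAP 14.5 and Table 14.3.5.3 all treat it separately.

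**The case against.** The strongest reply is that little depends on the PCI label. An abnormal lipase value still gets its H or L flag, enters Table 14.3.5.1 with minimum, maximum and change from baseline, and appears in the complete listings. Under SAP 12.2 the out-of-range post-dose result, not its repeat, goes into the summaries. Protocol 8.11.4 has confirmed abnormal results assessed for clinical significance and reported as adverse events where its criteria are met, without reference to Appendix A. Neither the stopping criteria (Protocol 7.6) nor the Part 2 decision (Protocol 7.5) is tied to PCI. All of this stands. A reader might infer that abnormal values would go unseen or that subjects are less protected; the documents do not support that.

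A reader might also infer that the drug's target organ is left unmonitored. Protocol 1.3 uses that term for the central nervous system. The pancreas is a main affected organ in rats, and the mechanism described is reduced insulin secretion. Glucose, the test closest to that mechanism, has limits both ways (−1.5 and +2.5 mmol/L), and amylase has an increase limit (+150 U/L). Pancreatic monitoring is therefore not outside the PCI rule.

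The magnesium and reticulocyte dashes may be deliberate. Appendix A comes from a standing form, leaves the limit to the Principal Investigator, and uses dashes for many other tests. The natural reading is that no limit was set, but the SAP does not say so. Even a deliberate dash would still produce an unexplained zero in Table 14.3.4. For lipase and LDL nothing points to a choice: amylase, total cholesterol, HDL and triglycerides all have limits.

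On coagulation, shell T_LB1 covers all tests, so aPTT and PT do belong in Table 14.3.4. The gap is the table's source reference and the missing listing; the documents do not show that coagulation is barred from the table.

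**Conclusion.** The point holds as a defect in the PCI table and listings. Four of 40 planned blood tests, all secondary safety endpoints, cannot be PCI at any value, and Table 14.3.4 would show a structural zero for each in every arm tested (up to seven). For lipase and LDL this follows directly from the missing rows. For magnesium and reticulocytes it rests on reading the undefined dash as no limit, which fits the one-sided rows such as ALT. The zero also assumes that Table 14.3.4 is programmed for all tests, as its shell instructs.

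The documents allow no estimate of how many abnormal values would be missed, because they give no expected rate. The coagulation gap is a separate, smaller inconsistency with SAP 14.5. Data capture, adverse event reporting and the primary analysis are unaffected. The correction should be made, but the trial does not depend on it.

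**What to change.** SAP 7.2 locks each part separately, so make these changes before the Part 1 lock to have them apply to both parts.

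- Have the Principal Investigator supply Appendix A change limits for lipase and LDL.
- For magnesium and reticulocytes, have the Principal Investigator either supply limits or confirm that none is intended, and define the dash in Appendix A.
- In Table 14.3.4, show any test left without a limit as 'not assessable' instead of zero.
- Add coagulation to the source of Table 14.3.4 and specify a coagulation PCI listing.

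Calling every new out-of-range value PCI for these four tests is not a good substitute. It is looser than the rule for other tests, and it misses a value that was abnormal at baseline and then worsens. As an illustration only, if 2% to 5% of results were newly out of range (an assumption), 1,680 results would give 1,680 × 0.02 ≈ 34 to 1,680 × 0.05 = 84 flags.

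The cost is a few Appendix A rows, one more listing and some additional flags. No new data are needed.

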13.1 Disposition of Subjects

The disposition of all subjects in the safety population will be summarized including: number of subjects randomized (or treated, for non-randomised groups); number completing the study, by treatment; and number discontinued from the study. The number of subject in each analysis population will be summarized by treatment.

All subjects who withdraw or are withdrawn from the study will be listed, by treatment, with the reason for withdrawal.

A listing of analysis populations will be provided.

13.2 Protocol Deviations

Before closing the database, data listings will be reviewed to identify any significant deviations and determine whether the data should be excluded from any analysis populations.

Major protocol deviations include subjects who:

- Entered the study even though they did not satisfy the entry criteria.
- Met the criteria for withdrawal from the study but were not withdrawn.
- Received the wrong treatment or incorrect dose.
- Received an excluded concomitant therapy.
- Received investigational product(s) past the expiration date.

In addition, subjects with minor time deviations (measurements taken outside the allowable windows) will be identified. Allowable time windows for pharmacokinetic samples and other procedures are given in section 8.8 of the study protocol.

13.3 Demographic and Baseline Characteristics

Demographic and baseline characteristics (e.g. physical examination, vital signs and ECGs) will be listed and summarised.

Subjects who take concomitant medication will be listed. All non-trial medication will be coded using the version of the WHO Drug Global that is current when the database is locked.

13.4 Treatment Compliance

Dates and times of dosing will be listed.

14 Safety Analyses

Summaries and listings of safety data will use the safety population.

14.1 Extent of Exposure

The dates and times of treatment dosing will be listed to indicate exposure to the study medication.

14.2 Adverse Events

Adverse events will be coded using the version of the Medical Dictionary for Regulatory Activities (MedDRA) which is current at the time of database lock (version 20.1 or higher).

All adverse events will be listed.

The number of subjects with at least one treatment-emergent adverse event (TEAE) will be tabulated by actual treatment and MedDRA system organ class. A treatment-emergent adverse event is defined as an event emerging during treatment having been absent pre-treatment or having worsened relative to pre-treatment¹.

For each of the following, the number of adverse events and the number of subjects with adverse events will be summarised:

- TEAEs by system organ class and preferred term
- TEAEs by system organ class, preferred term and severity
- Drug-related (“Related” as recorded by the Investigator) TEAEs by system organ class and preferred term

Subjects with more than one TEAE will be counted only once, at the greatest severity or causality, for each system organ class/preferred term. Multiple TEAEs in a subject will be counted once per system organ class and preferred term. Adverse events with missing severity and/or causality will be treated as severe and related, respectively.

Summaries will be sorted by system organ class and decreasing total incidence of preferred term.

14.3 Deaths, Serious Adverse Events and Other Significant Adverse Events

Deaths and serious adverse events will be listed separately (fatal events separate from non-fatal events). Other significant adverse events, as identified by the investigator in the CRF, will be listed separately.

14.4 Adverse Events Leading to Withdrawal from the Study

Adverse events leading to withdrawal will be listed separately.

14.5 Clinical Laboratory Evaluations

Data from haematology, coagulation, clinical chemistry and urinalysis will be summarised by treatment.

Urinalysis parameters will also be listed

All laboratory values of potential clinical importance will be listed and all related laboratory results (i.e. haematology or clinical chemistry) for subjects with values of potential clinical importance will be listed, separately. Frequencies of laboratory values of potential clinical importance will be summarised.

14.6 Other Safety Measures

14.6.1 Vital signs

Vital signs evaluation at each planned assessment, and change in vital signs from baseline (Day 0 pre-dose in the current treatment period) at each planned post-baseline assessment (with or without potential clinical significance) will be summarised by actual treatment.

Vital signs data of potential clinical importance will be listed.

